**PROTOCOL ABSTRACT**

Among people diagnosed with HIV/AIDS, the widespread use of highly active antiretroviral therapy (HAART) has greatly improved survival rates (Palella et al., 1998) and changed the leading causes of death, from AIDS-related diseases (e.g., non-Hodgkin's lymphoma, Kaposi sarcoma), to cardiovascular disease and lung cancer (Palella et al., 2006). As such, addressing modifiable risk factors for disease mortality among those with HIV/AIDS, including tobacco use, has become a critical priority (Nahvi & Cooperman, 2009). To date, only three smoking cessation clinical trials have been conducted with those with HIV/AIDS (Lloyd-Richardson et al., 2009; Vidrine et al., 2006; Ingersoll et al., 2007) none of which investigated the efficacy of FDA-approved medications for nicotine dependence. Varenicline is an  $\alpha 4\beta 2$  nicotinic acetylcholine receptor partial agonist with greater efficacy for treating nicotine dependence than bupropion (Gonzales et al., 2006; Jorenby et al., 2006) or nicotine patch (Aubin et al., 2008; Biazzo et al., 2010; Stapleton et al., 2008). Varenicline may be particularly efficacious for treating nicotine dependence among individuals with HIV/AIDS given that depression symptoms (Cruess et al., 2003) and cognitive impairment (Lindl et al., 2010) are common in this population, increase during smoking abstinence and predict smoking relapse (Zvolensky et al., 2009; Evans & Drobis, 2009), and are significantly reduced by varenicline (Patterson et al., 2009; Smith et al., 2009; Philip et al., 2009; Rollema et al., 2009). Therefore, we will conduct a randomized, double-blind, placebo-controlled trial of varenicline with smokers with HIV/AIDS. Specifically, 310 smokers with HIV/AIDS will be randomized to varenicline plus 9 weeks of smoking cessation counseling or placebo plus 9 weeks of smoking cessation counseling. The primary outcome variable for this study will be 7-day biochemically confirmed tobacco

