## CHARACTERISTICS OF THE STUDY POPULATION

### 1. Target Population

Three hundred ten adult male and female smokers 18 years of age or older who have been diagnosed with HIV/AIDS (identified through the UPENN CFAR Clinical Core, UPHS PennChart reviews and community-based HIV/AIDS organizations and events) and smoke at least 5 cigarettes per day will complete the study.

At PENN, a previous nicotine patch trial recruited a sample comprised of 45% women and 16% racial/ethnic minorities ([name] et al., 2010b). A separate PENN smoking cessation trial that used targeted efforts to recruit minority smokers had a sample comprised of 55% women and 52% racial/ethnic minorities ([name] et al., 2011). The UPENN CFAR Clinical Core population is 78% African American and 4% Hispanic American.

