### 2. Accrual

For this trial, we project that we will screen ~1000 HIV/AIDS patients over 54 months (allowing six months to complete follow-up), 77% of whom will be current smokers ( $n = 770$ ). Additional data indicate that upwards of three-quarters of these patients will want to quit smoking and will want to use a medication in their quit attempt (Drach et al., 2010), yielding a sample of ~575 patients to recruit. Based on past varenicline trials ([name] et al., 2011; Patterson et al., 2009) and the present inclusion/exclusion criteria, we expect ~two-thirds of these patients to be eligible for the trial ( $n = \sim 345$ ). To be conservative, given the possible health problems evident in this population of smokers, we will project  $\leq 20\%$  of participants will withdraw from the trial and  $\geq 80\%$  of subjects will complete follow-ups. As is advised in smoking cessation trials (Hughes et al., 2003), intent-to-treat will be used for primary analyses, with missing outcome data coded as smokers.

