## **2. Statistical Analysis**

### **Power**

Power is provided for the primary aims since the exploratory aim is hypothesis generating. Power calculations were all approximated as t- or z-tests (2-sided,  $\alpha = .05$ ), and conducted using PASS Software (Power and Sample Size, NCSS Software, Kaysville, UT).

Aim 1: The primary analysis is a comparison in week 12 and 24 cotinine-confirmed 7-day point prevalence quit rates between placebo and varenicline. For the week 12 comparison, we based our sample size selection on the expectation that quit rates in the placebo and varenicline arms would approximate those reported in past varenicline trials with the general population of smokers (i.e., placebo = 21.2%; varenicline = 50.3%; Gonzales et al., 2006). With a sample of 310, we have >90% power to detect a significant effect between our treatment arm. Notably, we have 80% to detect a difference in week 12 quit rates if the difference between treatment arms is as small as 15%, not 29% as found in Gonzales et al. (2006), since the effect for varenicline may be smaller in this sub-group of smokers. For the week 24 comparison, we based our sample size on the expectation that the quit rate in the placebo arm would be 14.5%, vs. 33.5% for varenicline (Gonzales et al., 2006). In this case, we have 85% power to detect a significant difference between treatment arms. However, we have 80% power to detect a difference between treatment arms if the treatment arm difference is only 15%, not the 19% reported in Gonzales et al. (2006), since the effect for varenicline may be smaller in this sub-group of smokers. Even though it may appear that we are over-powered for Aim 1, we require the proposed sample to conduct the non-inferiority analyses for Aim 2.

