Aim 2: The analyses are a comparison in week 12 and 24 differences in QOL and severe side effects. For QOL, the overall scale mean among HIV/AIDS patients is 58.3 (SD = 24.5, Range 14-100; Holmes & Shea, 1998). We have 80% power to detect a mean difference of 7.8 at any time-point between the treatment arms with the proposed sample of 310. For side effects, the analyses will involve a test of non-inferiority since we cannot use standard statistical tests and conclude that a non-significant comparison shows that the drug is safe (i.e., "the absence of evidence is not evidence of absence"). In our past study with varenicline, 61% of participants on varenicline reported no severe side effects, vs. 76% of participants on placebo, a 15% difference (Patterson et al., 2009). With the present sample size, we will have 80% power to detect similar equivalence between treatment arms in terms of the frequency of severe side effects over the course of the 12-week treatment, given that side effects are actually non-significantly different across the treatment arms.

Aim 3: The analyses will assess changes in affect and cognitive function as mediators of treatment arm effects at week 12 and 24. These measures are continuous difference scores. Our sample of 310 is well above the minimum sample of 200 recommended for models of this size (Haduk, 1987; Boosma & Gabrielli, 1985). The mediation hypothesis will examine the proportion of treatment effect explained (Lin et al., 1997; Vittinghoff et al., 2009), and will test each mediation hypothesis with a z-score generated using the delta method. Our sample of 310 gives us 80% power to observe small effects in a 1-sample test ( $\delta=0.20$ ) when testing at  $\alpha=0.05$ . There are four proposed mediating pathways (2 measures of affect and cognition, respectively) between treatment and outcome, so our type-1 error will be corrected to 0.0125. Our sample of 310 gives us 80% power to detect small to medium effects ( $\delta=0.19$ ) for changes in the proposed mediators, which we have seen in previous trials (Patterson et al., 2009; [name] et al., 2010a).

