### **Data Analysis**

[name] will oversee analyses which will be conducted using Stata, SAS, or R-Language software. Preliminary analyses will assess sample characteristics by treatment with chi-square or logistic regression (e.g., gender, dependence, depression). These variables will also be examined for their relationship to completion of outcome assessments. Variables related to treatment arm or completion of follow-ups will be included as covariates in analyses of study aims. Compliance measures will be evaluated across treatment arms, and controlled for in primary analyses. We will examine the correlation between self-report and pill count data and week 3 and 12 varenicline levels. Although we will use intent-to-treat as the primary method for

[figure not shown]
evaluating study aims, we will conduct a completers only analysis of study aims and examine study aims with participants lost to follow-up due to death excluded as done previously ([name] et al., 2003).

**Missing Data:** We will examine if the rate of missing data, primarily our smoking cessation outcome data, is related to a range of potential variables, including treatment arm allocation and HIV/AIDS-related, demographic, and smoking-related variables. Standard statistical methods will be used to identify possible correlates of missing data such as chi-square and regression. Variables found to be associated with the rate of missing data ( $p < .05$ ) will be included as covariates in the analyses of aims. In the event of items missing at random on measures, items will be imputed prior to calculating final scores using conditional means, estimated with an iterated version of Buck's method (Gleason & Staelin, 1975). Dropout and missed sessions present a more serious issue. The best way to deal with this is to avoid the problem in the first place by keeping subjects connected to the trial and motivated to complete measures. In our clinical trials, compliance and retention rates were >80% thanks to our close monitoring of participants and use of incentives to offset travel costs ([name] et al., 2008). Primary analyses will assume that all subjects for whom smoking outcome data are unavailable are smokers (intent-to-treat). This assumption, which is conventional in smoking cessation research, can attenuate the differences between study groups in quit rates. Thus, we will also conduct a "completers-only" analysis.

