**6. Risk/Benefit Assessment**

There is minimal risk for serious adverse events. The treatments and procedures used in this study have been shown to be relatively safe. Varenicline has also been studied in several clinical trials and shown to be safe and efficacious. Nevertheless, there are risks in participating in this trial, which are described above.

However, the risks of participating in this trial are offset by the potential benefits for participants and society. Participants who enroll in this trial will benefit from the knowledge that they are contributing in an important way to potentially furthering scientific knowledge concerning ways to improve treatment for smokers with HIV/AIDS. All smokers will receive behavioral counseling for smoking cessation. Half of the sample will receive varenicline. The trial results may support the use of varenicline for the treatment of nicotine dependence among those with HIV/AIDS, thereby reducing tobacco-related morbidity and mortality in this population.

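### The 80% power for a 7.8-point quality-of-life difference needs a score from all 310 participants; at the plan's own upper bound of 20% withdrawal it is about 70%

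*Combined protocol and SAP*

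**What the plan says.** The Power section sets the method for all aims: "Power calculations were all approximated as t- or z-tests (2-sided", alpha 0.05). For Aim 2 it gives the input "For QOL, the overall scale mean among HIV/AIDS patients is 58.3 (SD = 24.5, Range 14-100") and the result "We have 80% power to detect a mean difference of 7.8 at any time-point between the treatment arms with the proposed sample of 310". The QOL comparisons it names are at Weeks 12 and 24.

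The documents describe the figure of 310 in two ways:

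- The Protocol Abstract has "310 smokers with HIV/AIDS will be randomized to varenicline plus 9 weeks of smoking cessation counseling" or to the placebo equivalent. The Subjects paragraph of Study Procedures likewise makes 310 the number who are eligible and consent.
- The Target Population section says that 310 adults who have HIV/AIDS "and smoke at least 5 cigarettes per day will complete the study".

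On retention, the Accrual section projects, as a conservative figure, that at most 20% "of participants will withdraw from the trial and" at least 80% finish follow-up.

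On missing data, the Data Analysis section says "Primary analyses will assume that all subjects for whom smoking outcome data are unavailable are smokers (intent-to-treat"). For other measures it imputes single items before scoring. It treats dropout and missed sessions as a separate and harder problem, to be met mainly by retention efforts.

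**The concern.** Keeping all 310 in the denominator is legitimate for abstinence, because an absent participant is assigned an outcome. It does not carry over to the HAT-QoL, a self-report scale. A participant who does not complete it has no score, and item-level imputation cannot create one. The power claim covers any time-point, and so includes Week 24, by which time most withdrawal will have happened.

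QOL is one of the two parts of Aim 2 and has a directional hypothesis. If the claim stands, a null QOL result will be set against a sensitivity that the design has only with full retention. At the plan's own withdrawal bound, the chance of missing a true 7.8-point difference is about 30%, not 20%.

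**Working it through.** **Inputs.** SD 24.5, difference 7.8, two-sided alpha 0.05 and total 310 (Power section). Allocation 1:1, since "Half of the sample will receive varenicline" (Risk/Benefit Assessment), so n = 155 per arm. Withdrawal up to 20% (Accrual).

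**Formulas (normal approximation).**

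- Power = Φ( Δ / (SD·√(2/n)) − 1.960 )
- Difference detectable with 80% power = (1.960 + 0.842)·SD·√(2/n)

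**Step 1: reproduce the plan's figure.** With n = 155, the standard error is 24.5·√(2/155) = 2.783. Then 7.8/2.783 = 2.803, and Φ(2.803 − 1.960) = 80.0%. The noncentral t gives 79.8%. The detectable difference is 2.802 × 2.783 = 7.80. The printed figure is arithmetically correct, and it uses all 310 scores with no allowance for loss. A one-sided test would give 87.7%, so sidedness does not explain it.

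**Step 2: apply loss, equal in both arms.** At 20%, n = 124. The standard error is 24.5·√(2/124) = 3.111, 7.8/3.111 = 2.507, and Φ(2.507 − 1.960) = 70.8%.

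| QOL data lost | Scores observed | Power for 7.8 (z) | Power for 7.8 (t) | Difference at 80% power (z) |
|---|---|---|---|---|
| 0% | 310 | 80.0% | 79.8% | 7.80 |
| 10% | 279 | 75.8% | 75.5% | 8.22 |
| 15% | 263.5 | 73.4% | 73.1% | 8.46 |
| 20% | 248 | 70.8% | 70.4% | 8.72 |

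By the t distribution the last detectable difference is 8.75.

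**Step 3: test the completer reading.** For 310 to complete at 20% loss, 310/0.8 = 387.5, so 388 must be randomised. The Accrual section expects about 345 eligible. At 20% loss that leaves 345 × 0.8 = 276 scores and 75.3% power. At 10% loss it leaves 345 × 0.9 = 310.5, which matches 310 completers.

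**The case against.** **The figure contains no miscalculation.** This stands. The sentence states its N openly and the result reproduces. The fault is an unstated assumption of full retention.

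**310 may mean completers.** A reader might infer that the Accrual section rules this out. It does not. It gives no number randomised, and 345 eligible with 10% loss yields about 310. Its own fraction is also loose: two-thirds of 575 is 383, not 345, and 80% of 383 is 307. If 310 were completers, the power sentence would be right. But the Abstract and the Subjects paragraph say randomised or enrolled, and about 6 enrolments a month for 54 months is 324, well short of 388. The conflict lies between Target Population and those two places, and the documents leave it open.

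**20% is an upper bound.** This also stands. The plan offers it as conservative, cites retention above 80% in earlier trials, and allows assessments by telephone, so a missed clinic visit need not lose a score. None of this amounts to a projection of full retention.

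**The planned analysis is not a single-visit t-test.** QOL will be analysed by repeated-measures MANOVA with covariates. If Week 0 QOL were used as a covariate with an assumed correlation of 0.3, power at 248 would be 74.8%. At 0.5 it would be 82.5%, and about 0.45 would restore 80%, since 1 − 0.45² ≈ 0.8. The documents give no correlation, do not name baseline QOL as a covariate, and use neither in the stated power. MANOVA that drops anyone with a missed visit could also lose more than the Week 24 attrition alone, because QOL is collected at nine visits.

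**Conclusion.** The claim of 80% power at any time-point holds only if all 310 participants give a QOL score at the visit in question. With 310 randomised or enrolled and up to 20% withdrawing, power for 7.8 points lies between about 70% and just under 80%, and the 80%-power difference between 7.8 and about 8.7 points. This assumes SD 24.5, equal loss by arm, and the unadjusted single-visit comparison behind the plan's own figure.

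A reader might infer that the trial simply has 70% power for QOL at Week 24. The documents do not support that: 70% is the value at the worst retention the plan allows, no retention figure is given for Week 12, and power under the planned repeated-measures analysis cannot be computed from what is stated.

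The shift of about 0.9 points is modest and does not touch the abstinence endpoint. It does correct a figure that the plan gives for a named aim.

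**What to change.** First reconcile the Target Population section (310 completing) with the Protocol Abstract and the Subjects paragraph (310 randomised or enrolled). If 310 is the number of completers, the power sentence can stand, but the number to be randomised must then be stated.

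If 310 is the number randomised, replace the QOL power sentence under Aim 2 with:

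> With 310 randomised and QOL data from every participant, power is 80% for a 7.8-point difference in means. Allowing for up to 20% withdrawal (as few as 248 with QOL data), the difference detectable with 80% power rises to about 8.7 points, and power for 7.8 points falls to about 70%.

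Leave the sample size unchanged. The cost is one sentence and a slightly less favourable stated figure, with no extra participants and no change to procedures or analysis.

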### **Data Analysis**

[name] will oversee analyses which will be conducted using Stata, SAS, or R-Language software. Preliminary analyses will assess sample characteristics by treatment with chi-square or logistic regression (e.g., gender, dependence, depression). These variables will also be examined for their relationship to completion of outcome assessments. Variables related to treatment arm or completion of follow-ups will be included as covariates in analyses of study aims. Compliance measures will be evaluated across treatment arms, and controlled for in primary analyses. We will examine the correlation between self-report and pill count data and week 3 and 12 varenicline levels. Although we will use intent-to-treat as the primary method for

[figure not shown]
evaluating study aims, we will conduct a completers only analysis of study aims and examine study aims with participants lost to follow-up due to death excluded as done previously ([name] et al., 2003).

**Missing Data:** We will examine if the rate of missing data, primarily our smoking cessation outcome data, is related to a range of potential variables, including treatment arm allocation and HIV/AIDS-related, demographic, and smoking-related variables. Standard statistical methods will be used to identify possible correlates of missing data such as chi-square and regression. Variables found to be associated with the rate of missing data ( $p < .05$ ) will be included as covariates in the analyses of aims. In the event of items missing at random on measures, items will be imputed prior to calculating final scores using conditional means, estimated with an iterated version of Buck's method (Gleason & Staelin, 1975). Dropout and missed sessions present a more serious issue. The best way to deal with this is to avoid the problem in the first place by keeping subjects connected to the trial and motivated to complete measures. In our clinical trials, compliance and retention rates were >80% thanks to our close monitoring of participants and use of incentives to offset travel costs ([name] et al., 2008). Primary analyses will assume that all subjects for whom smoking outcome data are unavailable are smokers (intent-to-treat). This assumption, which is conventional in smoking cessation research, can attenuate the differences between study groups in quit rates. Thus, we will also conduct a "completers-only" analysis.

**Aim 1: Compare 12-weeks of varenicline treatment and behavioral counseling to 12-weeks of placebo treatment and behavioral counseling for treating nicotine dependence among individuals with HIV/AIDS.** We will analyze quit rates using mixed effects logistic regression. The model will include a term for time-point and, possibly, a *small number of covariates as needed*. The hypothesized effect of treatment arm (placebo vs. varenicline) will be tested by including a dichotomous term for treatment arm; we will also test for an interaction between time-point and treatment. Outcomes of the logistic regression analyses will be characterized by odds ratios (e.g., odds of quitting smoking) and 95% confidence intervals. Although quit-rates at the end of 12 and 24 weeks will represent our primary outcome variables, similar logistic regression analyses will be performed for other measures of quit rates, including prolonged and continuous abstinence. In addition, many participants will fail to become completely abstinent, but may show a reduction in smoking. A secondary analysis will examine the effect of treatment arm on daily cigarette counts using mixed effects negative-binomial regression. Likewise, time to (recurrent) event models will be fitted using Cox regression, stratified by event sequence, as in [name] et al. (2010b), to assess lapse and recovery events over 24 weeks.

**Aim 2: Assess effects of varenicline therapy on QOL and side effects.** Repeated-measures MANOVA will examine differences across treatment arms in QOL (total scale score and subscale scores) over the trial. Participant covariates will be included, such as medical treatment history. In addition, we will compare treatment arms in terms of the frequency of severe side effects (*individual, including cardiovascular side effects, and total*). Using logistic regression, we will test against the lower boundary on percent reporting only mild-moderate (i.e., < severe) side effects. The hypothesis test for equivalence is a test of whether the OR is out of the prescribed range for the difference between the treatment arms. This approach provides a more valid test of the potential safety of varenicline for individuals with HIV/AIDS vs. a simple comparison of mean responses on a side effects measure. *We will also examine if participants on tenofovir (vs. other HAART) experience a greater frequency or more severe varenicline side effects by including type of HAART as a covariate in these analyses and, if so, we can explore if this relationship is mediated by varenicline plasma levels using a regression-based path model. Lastly, we will also examine if the frequency of cardiovascular side effects is different between treatment arms while considering if participants are currently taking HAART or not by including a covariate for current HAART use in the logistic regression models of side effects.*

**Aim 3: Assess changes in affect and cognitive impairment as mediators of varenicline therapy's effect on quit rates.** We will use a regression-based path model approach to examine mediation of treatment effects based on MacKinnon et al. (2007). All variables will be standardized for the analyses. Candidate mediators include positive and negative affect and two cognitive performance task measures. Suspected mediators will be entered as standardized pre-post differences, continuously distributed and treated as normal in linear regression. The effects of treatment arm on mediators, and of mediators on outcome, will be assessed using linear regression and standardized variables. We will focus on changes in

mediators from baseline to week 3, since abstinence-induced withdrawal effects typically peak within the first 3 weeks of cessation (Hughes, 2007) but we can examine delayed changes to weeks 5, 7, and 9 as well. We will then assemble the path model using “seemingly unrelated estimation” methods (Beasley, 2008; Zellner, 1962). The path model partitions the effect of treatment on outcome into direct (and unexplained) effects vs. mediated effects. We will then test the overall mediation hypothesis using the proportion of treatment effect explained (Lin et al., 1997; Vittinghoff & McCulloch, 2009), and the strength of each mediating pathway as follows. We will estimate the model for standardized treatment predicting abstinence without mediators to estimate the direct effect of treatment in the unadjusted model ( $\beta^*$ ). We will then test whether treatment predicts each of the suspected mediators and, in turn, test whether mediators predict abstinence in an adjusted treatment model and estimate the effect of treatment in the mediator adjusted model  $\hat{\beta}^*$ . Finally, we will calculate the proportion of treatment effect explained, which is calculated as  $(\hat{\beta}^*/\beta^*)$ ; the standard error for this quantity is calculated using the delta method, and the mediation hypothesis will be tested using a z-test. Individual pathways will be tested using products of the coefficients along each path using a delta-method based z-test.

**Exploratory Aim: Explore participant-related variables as moderators of varenicline therapy's effect on quit rates.** These analyses will be hypothesis-generating. Variables will be chosen for this analysis based on their association with smoking behavior among those with HIV/AIDS (e.g., Webb et al., 2007). The significance of participant-related variables (e.g., mode of transmission, level of nicotine dependence, use of menthol tobacco) as moderators of varenicline's effect on quit rates can be evaluated by fitting logistic regression models relating quit rates to treatment arm and covariates. The likelihood ratio test can determine whether including such variables in the model contributes significantly to model fit. Evaluating the effect of treatment arm on quit rates by history of IV drug use, for example, is essentially doing a subgroup analysis of the interaction effect separately by such variables. To test the significance of a moderating influence of these variables, 2-way interaction terms can be added sequentially in steps of a hierarchical logistic regression model. A range of participant-related characteristics, such as socio-demographic (e.g., gender, race), psychiatric (e.g., depression), and medical (e.g., HIV/AIDS symptoms, method of HIV transmission) variables can be explored for potential interactions with treatment arm to influence quit rates at weeks 12 and 24.

**Additional Exploratory Analyses:** This trial will allow us to explore additional secondary hypotheses. One such analysis will focus on the assessment of whether HAART adherence is related to smoking cessation outcomes. [name], an expert in the assessment and evaluation of HAART adherence, will work with [name] to explore if response to varenicline, for example, affects HAART adherence or if HAART adherence is related to varenicline adherence. Prediction models of cessation outcomes (or varenicline adherence) using treatment arm and HAART adherence can be examined with logistic regression. We will also examine the relationship between 3-HC/cotinine and other variants in genes responsible for nicotine metabolism and drug target and response to varenicline for exploratory purposes.

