**Varenicline Adherence.**

At each session after Pre-Quit until end of treatment, participants are evaluated in terms of their adherence by self-report and pill count. At Weeks 3 (steady-state) and 12 (end of treatment), participants will be asked to provide blood samples to evaluate varenicline levels as a measure of adherence. Specific strategies to address non-adherence will be used if necessary. The varenicline adherence approach formally assesses participant reasons for non-adherence using scenarios and uses specific strategies to enhance compliance. If the participant discontinues study medication for any reason for 14 or more consecutive days prior to an adherence blood draw, the blood draw will not be conducted.

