#### Treatment Measures.

##### Varenicline Adherence

Varenicline adherence will be assessed by self-report using a time-line follow-back procedure and by pill count and the collection of used blister packs at each visit during the treatment period as done in past varenicline trials (e.g., Gonzales et al., 2006; Jorenby et al., 2006; Ebbert et al., 2009). We will also collect blood samples (10 mL) at Weeks 3 and 12 to assess varenicline levels as an additional measure of adherence and to examine the validity of self-report and pill count data. An adherence covariate will represent the proportion of total dose taken. These biosamples will be shipped to the laboratory of [name] at the University of California San Francisco for analysis. These blood samples will not be collected if the participant has not taken the study medication for 14+ days.

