##### Side Effects

As in our past varenicline trials (Patterson et al., 2009; [name] et al., 2011), a checklist and open-ended questions will assess the frequency and severity of varenicline-related side effects at all time-points after the Intake Session over the course of the 24-week study, before and after medication initiation. These assessments monitor participant safety and dose reductions or suspension can occur. Side effects will be a study outcome and can be a covariate in the analysis as the overall frequency and/or as the presence (ever) of specific side effects. This measure includes psychiatric events (e.g., depressed mood, suicidal ideation; Kuehn, 2008) and cardiovascular side effects.

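### The primary analyses are to be adjusted for study-drug compliance, a post-randomisation variable, so the arm odds ratio would no longer estimate the effect of assignment

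*Combined protocol and SAP*

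**What the plan says.** The opening paragraph of Data Analysis makes an unconditional commitment: "Compliance measures will be evaluated across treatment arms, and controlled for in primary analyses". The covariate is defined under Treatment Measures, Varenicline Adherence: "An adherence covariate will represent the proportion of total dose taken". Its timing is given under Study Procedures, Varenicline Adherence: "At each session after Pre-Quit until end of treatment, participants are evaluated in terms of their adherence by self-report and pill count". Drug is first dispensed at the Pre-Quit session, so all of these measurements follow randomisation.

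Other sections point to a different analysis:

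- Accrual: "intent-to-treat will be used for primary analyses, with missing outcome data coded as smokers". Data Analysis repeats that intent-to-treat is the primary method.
- Power, Aim 1: "The primary analysis is a comparison in week 12 and 24 cotinine-confirmed 7-day point prevalence quit rates between placebo and varenicline". No compliance term is mentioned.
- Data Analysis, Aim 1: a mixed effects logistic model with arm, time-point, their interaction and, possibly, a "small number of covariates as needed". Compliance is neither named nor ruled out.

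**The concern.** Randomisation makes the arms comparable at baseline. It does not make them comparable among people who took the same proportion of their tablets, because the assigned arm can change how many tablets are taken. If people who are going to quit also tend to take more doses, conditioning on doses taken mixes that association into the arm odds ratio.

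The documents give a reason to expect different adherence by arm. For an earlier study the Power section reports that "61% of participants on varenicline reported no severe side effects, vs. 76% of participants on placebo, a 15% difference", and the Side Effects section says that "dose reductions or suspension can occur".

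Two things are at stake. First, two analysts could each follow the plan and report different primary odds ratios, one adjusted for compliance and one not. Second, the adjusted one could show an effect that is absent or hide one that is present, and the direction cannot be known beforehand.

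**Working it through.** The plan states no figure for this adjustment, so there is none to reproduce. The check is a reading of the text followed by simulation to show scale.

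**Inputs from the documents.** 310 randomised, half to varenicline, so 310 / 2 = 155 per arm; two-sided 5% test; placebo quit rate 21.2% at week 12 and 14.5% at week 24; a smaller effect of 15 points (21.2% v 36.2%) and the expected effect of 21.2% v 50.3%; severe side effects 100 − 61 = 39% on varenicline and 100 − 76 = 24% on placebo.

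**Assumed inputs, not in the documents.** Adherence = 0.60 + gap × abstinent + shift × varenicline + normal error (SD 0.25), limited to 0–1. *Gap* is how much more of their doses quitters take; *shift* is the arm difference. Each simulated trial has one time-point and a logistic regression with and without adherence, with a Wald test of arm. This simplifies the two-time-point mixed model. There were 2,000 trials per cell and 6,000 for key cells; simulation error is about 0.3 to 1.1 points.

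**Step 1. No true effect (21.2% in both arms), adjusted model.**

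| Gap | Shift | Type I error |
|---|---|---|
| 0.10 | 0 | 4.5% |
| 0.25 | 0 | 4.3% |
| 0.10 | −0.05 | 5.9% |
| 0.10 | −0.10 | 9.0% |
| 0.25 | −0.05 | 10.1% |
| 0.25 | −0.10 | 23.5% |
| 0.25 | +0.10 | 21.1% |

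With no shift the null odds ratio is 1.0. With shifts of 5 to 10 points and gaps of 10 to 25 points it runs from 0.69 to 1.48. At the week 24 placebo rate of 14.5%, type I error over that range is about 5 to 20%.

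**Step 2. True 15-point effect.** The unadjusted odds ratio is (0.362/0.638) / (0.212/0.788) = 0.567/0.269 = 2.11, with power 83%. Adjusted power:

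| Gap | Shift 0 | Shift +0.05 | Shift +0.10 |
|---|---|---|---|
| 0.10 | 82% | 73% | 61% |
| 0.25 | 76% | 50% | 25% |

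At shift +0.10 the odds ratio falls to between 1.45 and 1.81. At shift −0.10 with gap 0.25 it is overstated at 3.14.

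**Step 3. Expected effect, 21.2% v 50.3%.** Adjusted power is still 92 to 93% in the worst cell (gap 0.25, shift +0.10).

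**Step 4. The side-effect route.** Adherence = 0.75 + gap × abstinent − loss × severe side effect + error, with severe side effects at 24% and 39% and loss of 0.20 to 0.67 (assumed). The expected arm difference is 0.15 × 0.20 = 3 points to 0.15 × 0.67 = 10 points before limiting adherence to 0–1, and about 3 to 9 points after. Type I error is 5 to 9% and the null odds ratio 1.05 to 1.15. With a true 15-point effect, power rises slightly (85 to 92%) and the odds ratio is inflated from 2.11 to about 2.2 to 2.4.

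**Step 5. A different mechanism.** Here an unmeasured factor such as motivation raises both a yes/no compliance measure and quitting. Assumed compliance is 66% on placebo and 50% or 79% on varenicline. The null odds ratio becomes 1.12 (compliance lowered) or 0.90 (raised). Type I error is 5.9 to 6.1%, against 4.5 to 5.3% unadjusted. With equal compliance the null odds ratio is 1.00.

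**The case against.** The strongest objection is to size. The large figures depend on an assumed adherence baseline of 0.60 and on generating adherence directly from the outcome. With a baseline of 0.80 the worst cells shrink: type I error 17 to 18%, null odds ratio 0.75 to 1.39, lowest power 37%. The shared-cause model gives only about 6%. The one documented reason for an arm difference implies lower adherence on varenicline, whereas the power losses need higher adherence. Adherence is collected only to week 12, so tying it to week 24 abstinence is a further simplification. All of this stands: the 24% and 25% extremes show what is possible, not what is expected.

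A second objection is that the plan applies intent-to-treat mainly by counting missing outcomes as smoking, and adjustment excludes nobody. That is correct for pill-count or self-report adherence. The conflict is over what is estimated, not over who is analysed. Aim 1 asks about varenicline plus counselling against placebo plus counselling, and conditioning on doses taken answers another question.

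A third is that the specific Aim 1 paragraph should govern, and that it can be read as leaving compliance out. It leaves the covariates open, however, while the general paragraph is unconditional. Nothing withdraws that commitment or labels the adjusted analysis as secondary.

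**Conclusion.** The concern holds. As written, the plan commits the primary analyses to a covariate that treatment assignment can change, and it guarantees no primary estimate free of that covariate. This follows from the text and needs no particular figure.

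The size is uncertain. If adherence is the same in both arms, the false-positive rate is unaffected, though power for a 15-point effect can fall to between 76 and 82%. If the arms differ, the bias ranges from slight (the side-effect and shared-cause models) to serious (a 10-point arm difference with a 25-point quitter gap). Under the plan's expected 29-point effect the trial would very probably still detect a difference. The risk is greatest at the 15-point effect that the Power section itself allows for in this population. Since this is the primary estimate of a Phase III trial and the direction of bias is unknown in advance, the text must be corrected.

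**What to change.** In the opening paragraph of Data Analysis, delete the clause that commits the primary analyses to control for compliance; keep the comparison of compliance across arms. In the Aim 1 paragraph, state that the primary model compares arms as randomised, adjusts only for baseline covariates specified in advance, and contains no variable measured after randomisation. This also keeps out the optional side-effects covariate described under Side Effects. Report any compliance-adjusted analysis as a labelled secondary analysis.

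The rules in Data Analysis and Missing Data that add covariates according to their observed relation to arm, follow-up completion or missingness should be brought into line with this wording.

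The cost is wording only: no data or participants are lost, and the adherence-adjusted estimate moves to a secondary table. Because this is Version 19, dated February 2018, and the study biostatistician may present unblinded results to the DSMB, the change should be dated and documented relative to unblinding.
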